8.1 Pharmacokinetic Analysis

Plasma concentrations, time of sample collection and time post-dose calculations will be listed. Concentrations may be part of a population PK analysis that will be reported separately.

8.2 Pharmacodynamic Analysis

A by-subject listing of all PD variables, including erythropoietin (EPO), reticulocytes, and iron indices (iron, ferritin, TIBC, and TSAT), will be provided including the changes from Baseline/Day 1. The observed and change from Baseline/Day 1 values of all PD assessments will be summarized using descriptive statistics. For PD variables analyzed after database lock, values will be reported separately.

8.3 Pharmacogenomic Analysis

No PGx analysis is planned.

9 Efficacy Endpoints and Analyses

The general approach for analysis of continuous outcomes will be analysis of covariance (ANCOVA) with multiple imputation for missing data or mixed models for repeated measurements (MMRM) on observed data.

For binary variables, the general approach will be Mantel-Haenszel estimation of risk difference stratified by the baseline strata with (or without) multiple imputation for handling missing data [Mantel, 1959].

9.1 Primary Estimand

The primary estimand defining the treatment effect of interest in this trial uses the treatment policy strategy specified in the ICH E9 (R1) Addendum [FDA 2021b]. In this trial, the research question is to compare the assignment of darbepoetin alfa to vadadustat, regardless of intercurrent events. The primary analysis will be performed in the randomized population in accordance with intent-to-treat. This means the analysis will include individuals who never received treatment, discontinued treatment, were rescued with any therapy, and withdrew consent. The estimate of the treatment effect of interest will be the one regardless of whether the intercurrent event occurred.

The primary estimand for this trial is defined by the following components:

- Treatment: vadadustat with rescue therapy as needed versus darbepoetin alfa with rescue therapy as needed.
- Population: randomized population.
- Variable: change in Hb from Baseline to the primary evaluation period (average Hb from Weeks 20 to 26, inclusive).
- Intercurrent event: never received treatment, discontinued treatment, rescued with any therapy or withdrew consent.
- Population-level summary: difference in mean change in Hb from baseline to the primary evaluation period between the vadadustat groups and darbepoetin alfa control group.

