## **7.3 Individual Subject Discontinuation**

During this trial, it is anticipated that some subjects may permanently discontinue IMP (vadadustat or darbepoetin alfa).

Subjects who discontinue IMP prematurely and the investigator determines that the subject will be permanently discontinued from the trial (see [Section 7.3.1](#)), will complete the ET Visit assessments and the Safety Follow-up Visit, 4 weeks after ET Visit.

Subjects may discontinue prematurely from the trial for any of the following reasons:

- Adverse Event.
- Subject withdrawal of consent.
- Investigator's discretion.
- Lack of efficacy, defined as inadequate response to darbepoetin alfa or vadadustat in the investigator's opinion.
- Lost to follow-up despite reasonable efforts by the investigator to locate the subject.
- Receipt of a solid organ (including kidney), hematopoietic stem cell, or bone marrow transplantation.
- Meeting criteria for Trial Medication Stopping Rules (see [Section 7.3.2](#)).
- Change in dialysis modality (ie, from hemodialysis to peritoneal dialysis or change from in center hemodialysis to home/nocturnal hemodialysis).
- Permanent change in frequency of in-center hemodialysis from three-times per week.
- Death.
- Other reasons (pregnancy [see [Section 10.3](#)], specific reasons to be documented by the investigator).

A subject has the right to withdraw consent for participation in the trial at any time ([Section 7.3.4](#)).

See [Table 7.3.2-1](#) for additional details on the management of subjects with ALT and AST abnormalities.

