#### **9.4.1.1.1 Primary Estimand**

The primary estimand defining the treatment effect of interest in this trial uses the treatment policy strategy specified in the ICH E9 (R1) Addendum. In this trial, the research question is to compare the assignment of darbepoetin alfa to vadadustat, regardless of intercurrent events. The primary analysis will be performed in the randomized population in accordance with intent-to-treat. This means the analysis will include individuals who never received treatment, discontinued treatment, were rescued with any therapy, and withdrew consent. The estimate of the treatment effect of interest will be the one regardless of whether the intercurrent event occurred.

The primary estimand for this trial is defined by the following components:

- Population: randomized population.
- Variable: change in Hb from Baseline (average pretreatment Hb) to the primary evaluation period (average Hb from Weeks 20 to 26, inclusive).
- Intercurrent event: never received treatment, discontinued treatment, rescued with any therapy, or withdrew consent.
- Population-level summary: difference in mean change in Hb from baseline to the primary evaluation period between the vadadustat groups and darbepoetin alfa control group.

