9.2.2 Hb in the Primary Efficacy Period

Hb for the PEP will be calculated as the average of all Hb measurements from the central laboratory within the three visit windows during Weeks 20 through 26, regardless of intercurrent events. At least 1 Hb measurement is required for the calculation; otherwise, the value will be missing and therefore imputed. The PEP is also called analysis time period 3 (see [Table 1](#)).

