9.2.4 Analysis of Change from Baseline in Hb to the Primary Efficacy Period

The primary analysis will use multiple imputation with ANCOVA as the substantive model and will be performed in the randomized population.

All intercurrent events will be handled by treatment policy strategy (see [Section 9.1](#)). Unobserved data after intercurrent events, including hemoglobin outcomes and any covariates to be used in the models, will be imputed with randomized subjects using multiple imputation under fully conditional specification (FSC) method. Under the assumption of FSC, data for each variable with missing values will be imputed with a separate regression model allowing for all available data to be used in the imputation process. For continuous variables, the regression method will be used for imputations. For categorical variables, logistic regression models will be used for binary outcomes, and nominal response logistic regression for nominal responses.

An ANCOVA model will be used to compare the mean change from baseline in Hb between 2 treatment groups with the complete dataset from multiple imputation. The ANCOVA model will contain treatment group, baseline Hb level, and the 2 stratification factors (geographic region and mean weekly darbepoetin alfa dose prior to Screening Visit 2) as predictor variables. The stratification factor assignments at randomization will be used in the analysis.

The data will have shown noninferiority of vadadustat if the lower bound of the 95% confidence interval for the difference in estimated change from baseline in the 2 groups (vadadustat minus darbepoetin) exceeds the noninferiority margin of -0.75g/dL. This ensures a 1-sided alpha of 0.025 for the primary analysis. If the lower limit of the 2-sided 95% confidence interval for the difference between the mean in the vadadustat group and the mean in the darbepoetin alfa group is above zero, superiority will have been established and the finding will be interpreted as providing evidence of a greater change from baseline in Hb for vadadustat relative to the control arm.

The procedure of primary analysis follows these steps:

- 1) Missing data will be imputed separately for each treatment group using FSC method with 100 imputed datasets and 40 iterations from PROC MI. The SAS codes of PROC MI with outcome variables and covariates will be as follows.

[REDACTED]

[REDACTED]

[REDACTED]

[REDACTED]

[REDACTED]

[REDACTED]

[REDACTED]

[REDACTED]

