9.4 Other Efficacy Endpoints: Strategies for Analysis

Except for specifying the analysis population, other efficacy endpoints analyses will be performed using the randomized and full analysis population, with the assigned treatment as described in [Section 3.1](#). There will be no correction for multiplicity for these endpoints.

9.4.1 Proportion of Subjects Having Average Hb Values within the Target Range during the PEP (Weeks 20 to 26)

All subjects will be defined as either being in their geography-specific target range (see [Section 2.3](#)) in Weeks 20 through 26 (“yes”) or not (“no”), based on the average Hb value during the three visit windows in Weeks 20 through 26. Subjects with no Hb value in the PEP value will be treated as missing. To ensure uniformity across all analyses, the missing binary outcomes will be computed from the imputed complete dataset in primary analysis (see [Section 9.1.4](#)) [Ratitch, 2013].

The proportion of subjects within target range will be calculated, and a 95% confidence interval of the proportion will be performed by treatment group.

A Mantel-Haenszel estimation of risk difference stratified by the baseline strata will be conducted, and the corresponding 2-sided 95% confidence interval for the risk difference will be calculated. Noninferiority will have been established if the lower limit of the confidence interval is above -15% when tested per the testing procedure ([Section 9.5](#)).

If the lower limit of the 2-sided confidence interval for the risk difference is above zero, superiority will have been established and the finding will be interpreted as providing evidence of a higher proportion of subjects being within the target range for vadadustat relative to the control arm when tested per the testing procedure ([Section 9.5](#)).

The associated odds ratio and corresponding 2-sided 95% confidence interval will also be calculated.

The analysis of proportion of subjects within target range follows these steps:

9.4.2 Proportion of Subjects Having Average Hb Values within the Target Range during the SEP (Weeks 46 to 52)

Proportion of subjects having average Hb values within the target range during the SEP (Weeks 46 to 52) will be analyzed using the same methodology as specified for the PEP (see Section 9.4.1).

9.4.3 Proportion of Subjects Receiving IV Iron Therapy from Baseline to Week 52

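### Under the visible rules, subjects who die before an evaluation window have Hb imputed and can be counted as within target range in noninferiority steps 5 to 8

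*SAP*

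**What the plan says.** The SAP's estimand (9.1) reads "Intercurrent event: never received treatment, discontinued treatment, rescued with any therapy or withdrew consent", and the Protocol's (9.4.1.1.1) gives the same four events: "Intercurrent event: never received treatment, discontinued treatment, rescued with any therapy, or withdrew consent". SAP 9.2.4 adds: "All intercurrent events will be handled by treatment policy strategy". Death does appear in Protocol 7.3, in the list that opens "Subjects may discontinue prematurely from the trial for any of the following reasons", and in the safety summaries of SAP 10.1 and 10.4.

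On missing Hb, SAP 9.2.2 needs at least one central-laboratory value in the primary window; "otherwise, the value will be missing and therefore imputed". SAP 9.2.4 says "Unobserved data after intercurrent events, including hemoglobin outcomes and any covariates to be used in the models, will be imputed with randomized subjects", and its first step is "Missing data will be imputed separately for each treatment group using FSC method with 100 imputed datasets and 40 iterations from PROC MI". No reason for missingness is exempted.

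On the target-range endpoint, SAP 9.4.1 says "the missing binary outcomes will be computed from the imputed complete dataset in primary analysis". (Its cross-reference is to 9.1.4; the imputation is in 9.2.4.) SAP 9.4.2 applies the same method to Weeks 46 to 52. SAP 9.5 makes these proportions steps 5 to 8 of the formal hierarchy, and 9.4.1 sets the margin at -15% and allows a superiority reading.

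**The concern.** A treatment policy strategy uses the outcome whether or not the event occurred. After death there is no Hb to use, so the strategy has no content for it. The general missing-data rule then fills the gap with a modelled value, and the binary endpoint turns that value into a success or a failure. In hemodialysis patients followed for a year, deaths are foreseeable: the plan adjudicates all-cause mortality.

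At stake are four formal noninferiority conclusions about Hb control. An arm's success rate can include subjects who were not alive in the window, and an arm with more deaths need lose nothing for it. This differs from the usual missing-at-random question for living subjects who leave, whose later Hb exists but was not measured.

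**Working it through.** **Tracing one subject.** SAP Table 1 opens the primary window on Day 127 and the secondary window on Day 309. A subject who dies at Week 10 (about Day 70) has no Hb in either. By 9.2.2 and 9.2.4 the value is imputed within arm in 100 datasets. By 9.4.1 the subject is in range in every dataset where the average falls in 10.0-11.0 g/dL (US) or 10.0-12.0 g/dL (Europe).

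**Planned analyses that might remove this.** The table list in SAP 19 gives target-range results only for the randomized population and the FAS (14.2.3.1.1 to 14.2.3.2.2). The FAS needs one dose and one post-dose Hb, so it keeps many early deaths. SAP 9.2.5 has no analysis specific to death.

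**The plan's own figure.** The only stated power is for change in Hb: more than 90% with about 100 per arm, SD 1.2, margin 0.75 and 30% dropout. With 70 evaluable per arm, SE = 1.2 x sqrt(2/70) = 0.203, and power = Phi(0.75/0.203 - 1.96) = 95.9%. It reproduces and is not in dispute. No power or event rate is stated for the target-range endpoint.

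**Size for the target-range endpoint (assumed inputs).** Let d be the share of an arm that dies with no Hb in the window, q the in-range probability of the other subjects, and q* the in-range probability of the values imputed for those who died.

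- Proportion as planned: (1 - d)q + d q*
- Proportion with those deaths scored not in range: (1 - d)q
- Gap within an arm: d q*
- Shift in the risk difference, vadadustat (V) minus darbepoetin alfa (D), with common q*: -(d_V - d_D) q*

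For d = 3-15% and q* = 0.4-0.6, the deceased subjects counted in range per 100 run from 100 x 0.03 x 0.4 = 1.2 to 100 x 0.15 x 0.6 = 9.0.

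For a 5-point mortality difference, the shift is 0.05 x 0.40 = 2 points to 0.05 x 0.60 = 3 points. That is 2/15 = 13% to 3/15 = 20% of the margin.

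**Chance of meeting the margin.** With 100 per arm, unstratified, imputed values treated as full information, and q = q* = 0.5, the chance is Phi((0.15 + RD)/SE - 1.96):

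| Deaths, V v D | Scoring of those deaths | RD | Chance |
|---|---|---|---|
| any | imputed, as planned | 0 | 56% |
| 5% v 5% | not in range | 0 | 57% |
| 10% v 5% | not in range | -2.5 points | 43% |
| 5% v 10% | not in range | +2.5 points | 70% |

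For the third row: proportions 0.450 and 0.475, SE = sqrt((0.2475 + 0.2494)/100) = 0.0705, (0.15 - 0.025)/0.0705 - 1.96 = -0.19, Phi = 0.43.

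**Size for change in Hb.** Including imputed values moves an arm mean by d x (imputed mean minus survivor mean). Suppose that gap were a full SD, 1.2 g/dL, in both arms, with 10% v 5% deaths. The arm difference would move by 0.05 x 1.2 = 0.06 g/dL, or 8% of the 0.75 margin.

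**The case against.** Much of the case on the other side stands, and it rules out several stronger readings.

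- **That the omission from the list causes the imputation.** It does not. The rule in SAP 9.2.2 covers any missing value, and death could be read as a form of discontinued treatment. Adding the word to the list would change no result. What is missing is a strategy.
- **That deceased subjects are credited at the survivors' rate.** The documents do not say so. Fully conditional imputation can use a subject's own earlier Hb, so someone whose Hb was falling may draw low values. The 40-60% is an assumption about q*, not a consequence of the method.
- **That every death in the window is affected.** One in-window Hb suffices, so a death after such a value is scored on real data.
- **That the rule favours vadadustat.** The direction depends on which arm has more deaths, and the documents give no rates.
- **That the primary result is exposed.** The effect there is small. For Weeks 20 to 26 the per-protocol analysis requires an Hb in the window, and the MMRM uses observed data only. Coverage is partial: per-protocol membership is set by the primary window, so it keeps subjects who die between the two windows, and the MMRM still treats visits after death as missing data.
- **That the plan is definitely wrong.** The PROC MI code and the target-range steps are redacted. A death rule there cannot be excluded.

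Two further points count for less. Steps 5 to 8 concern other efficacy endpoints and are reached only if steps 1 to 4 succeed; SAP 9.4 even says these endpoints get no multiplicity correction. But 9.5 lists them as formal tests and 9.4.1 refers to that procedure. It is also true that scoring death as a failure is a choice of estimand. Some choice is needed, because the current one is made by default.

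**Conclusion.** The point holds on the visible text, in limited form. Death has no stated strategy, and the general imputation rule lets a subject who died before the window count as in range in steps 5 to 8. No listed target-range analysis would show how much this matters.

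The size rests wholly on assumed rates: 2 to 3 points of risk difference for a 5-point mortality imbalance with 40-60% of imputed values in range, against a 15-point margin, in either direction. If deaths and q* are similar across arms, both proportions are inflated and the difference is about unchanged. A reader might infer that the primary noninferiority conclusion is unsafe or that the design tilts towards vadadustat; the documents support neither. This is a cheap improvement, subject to any death rule in the redacted code.

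**What to change.** 1. In SAP 9.1, name death as an intercurrent event with its own strategy for each endpoint. For change in Hb, say that values imputed after death are hypothetical.
2. In SAP 9.4.1 and 9.4.2, score a subject who died on or before the last day of the window (Day 196 or Day 378) with no Hb in it as not within target range. Keep the observed average for anyone who died after an in-window Hb; failing every death in the window would overwrite real measurements.
3. Report the current imputation-based result as a sensitivity analysis.
4. Give, per arm and window, the number of deaths with imputed Hb.
5. If the redacted code already has a death rule, state it in the text instead.

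The cost is a few sentences and one flag. No new data are needed, since deaths are already reported and listed. The downsides are slightly lower in-range proportions and an endpoint that becomes partly a composite with mortality. Deaths after a subject has left the trial and completed the safety follow-up may be unknown, so the rule applies to recorded deaths only.

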9.2 Definition of Primary Efficacy Endpoint: Change from Baseline in Hb

The primary efficacy endpoint is the change in average Hb between baseline and the PEP (Weeks 20 to 26, inclusive).

The primary analysis will use the randomized population with an ANCOVA, with randomization stratification factors and baseline Hb as covariates.

A 2-sided, 95% CI will be calculated for the difference in mean change in Hb from baseline to the PEP between the vadadustat group and darbepoetin alfa control group. Noninferiority of vadadustat will be established if the lower limit of this CI is ≥ -0.75 g/dL.

A hierarchical testing scheme will be used to correct for the multiplicity of the 2 primary endpoints: comparison between vadadustat QD vs. darbepoetin alfa and comparison between vadadustat TIW vs. darbepoetin alfa.

- Step 1: comparison between vadadustat QD vs. darbepoetin alfa.
- If the noninferiority of vadadustat is established in step 1, then move to the step 2;
- Step 2: comparison between vadadustat TIW vs. darbepoetin alfa.

9.2.1 Baseline Hb

Baseline Hb will be calculated as the average of the last 2 central laboratory Hb measurements of samples taken at the visits prior to or on the date of first dose date. If there is only one available Hb value prior to or on the date of first dose date, then it will be used for the calculation of baseline. If there is more than one available Hb values, the last 2 Hb values prior to or on the date of first dose date will be used.

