- Low darbepoetin alfa dose group ( $\leq 0.45 \text{ } \mu\text{g/kg/week}$ ): vadadustat 300 mg QD, 600 mg TIW.
- High darbepoetin alfa dose group ( $> 0.45 \text{ and } \leq 1.5 \text{ } \mu\text{g/kg/week}$ ): vadadustat 450 mg QD, 750 mg TIW.

Refer to the trial-specific Dosing Guideline for instructions on ESA medications conversion to an equivalent darbepoetin alfa dose for stratification and randomization.

Adjustments to doses for vadadustat will be guided by Hb concentration and Dose Adjustment Algorithms ([Section 6.1.1](#)).

For subjects who were receiving darbepoetin alfa during screening and randomized to the darbepoetin alfa treatment arm, the initial dosing regimen in the trial (starting from Baseline/Day 1) will be approximately the same weekly dose that they were receiving prior to randomization. Darbepoetin alfa dose will be administered IV at the hemodialysis clinic. For subjects receiving darbepoetin alfa for the first time, the initial dosing regimen (starting from Baseline/Day 1) will be determined by the US Package Insert (USPI) or European Union (EU) Summary of Product Characteristics (SmPC), per the medical

judgement of the investigator. Dose adjustments will be guided by the USPI or EU SmPC ([Section 6.1.1.4](#)). ESA dosing is independent of the visit schedule, and the dosing schedule may shift per local standard of care and investigator discretion.

Investigators will prescribe iron supplementation (IV, oral, or intradialytic) as needed during the trial to maintain ferritin  $\geq 100$  ng/mL or transferrin saturation (TSAT)  $\geq 20\%$  (see [Section 6.5.2.1](#) for details regarding iron supplementation during the trial). Subjects already receiving oral iron supplementation as part of their treatment plan may continue their current treatment regimen. Because of the potential for oral iron to reduce the bioavailability of vadadustat, the IMP is not to be administered concurrently with an oral iron supplement (including multivitamins containing iron), iron containing phosphate binders, or any oral medications containing iron.

Subjects will be instructed to take vadadustat at least 1 hour before oral medications containing iron ([Section 6.5.2.1](#)).

Clinical and safety assessments will be performed as indicated at Screening, during the Conversion and Maintenance Period, and during the Follow-up Period (4 weeks after the EOT) as shown in the Schedule of Assessments ([Table 1.3-1](#)).

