## **9 Statistical Considerations**

Data collected throughout the trial will be summarized using descriptive statistics and listed in by-subject listings. Continuous variables will be summarized using number of subjects with data, mean, standard deviation, median, minimum, and maximum. For categorical variables, the number and percentage of subjects in each category will be tabulated. Summaries will be provided by treatment group within appropriate analysis populations (as defined in [Section 9.2](#)) and by time point/time period, as appropriate.

For Hb, Baseline will be calculated as the average of the last 2 central laboratory Hb measurements of samples taken at or prior to the date of randomization. For other parameters, unless otherwise specified, Baseline will be defined as the last available value prior to the first dose of IMP.

Hemoglobin values will be assessed through the central laboratory for dose adjustments, efficacy, and safety evaluations.

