4.3 Baseline Characteristics, Exposure, and Retention by Treatment Group

Descriptive statistics will be generated by treatment group for demographic and pretreatment variables for each analysis population.

The total number of randomized subjects, treated subjects, and randomized but not treated subjects will be tabulated by treatment group in the randomized population.

The number of subjects who discontinued the study and the reason for discontinuation will be summarized for randomized population.

Medical history terms will be coded using the Medical Dictionary for Regulatory Activities (MedDRA) and summarized by system organ class (SOC) and preferred term (PT) for each treatment group based on the safety population.

5 General Conventions

Study days are defined as follows:

Study Day = [Event date – First dosing date + 1] if on or after first dosing date
[Event date – First dosing date] if before first dosing date.

Note that with the definition above, days of “0” will not be used. As such, the study day can be interpreted as the number of days before or after first day of dosing. Event date refers to the date associated with the result being summarized. In some cases, this is the date of an assessment or measurement; in other cases, this is the onset date of an adverse or outcome event.

For subjects whose reference date is missing, the study day will also be categorized as missing.

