	Week 34	Day 238	Day 225-252
	Week 38	Day 266	Day 253-280
	Week 42	Day 294	Day 281-308
5) Secondary Efficacy Period (SEP) (Weeks 46-52)	Week 46	Day 322	Day 309-336
	Week 50	Day 350	Day 337-357
	Week 52	Day 364	Day 358-378
Safety Follow-up	Follow-up	ET/EOT + 4 Weeks	ET/EOT+15 Days – ET/EOT+42 Days

ET=Early Termination; EOT=End of Treatment.

^a If patient has no first dose date, day 1 will be the randomization date.

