5.2 Definition of Baseline

The baseline value must be assessed prior to initiation of study treatment. For Hb, baseline will be calculated as an average of the last 2 values prior to or on the first dose date, as specified in [Section 9.2.1](#). For other parameters, unless otherwise specified, baseline will be defined as the last available value prior to the first dose of IMP.

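### The SAP takes baseline Hb and the efficacy windows from the first dose, while the protocol takes baseline from randomization, so a late first dose could put a post-randomization Hb into baseline

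*SAP*

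**What the plan says.** Protocol 9 averages the last two "central laboratory Hb measurements of samples taken at or prior to the date of randomization". SAP 5.2 says that "baseline will be calculated as an average of the last 2 values prior to or on the first dose date", and SAP 9.2.1 repeats this with "samples taken at the visits prior to or on the date of first dose date". SAP 5.1 also maps every assessment to a visit window by its distance from the first dose. Its revision table (SAP 20) shows that the windows were moved there on purpose, from the randomization date. Where the documents differ, SAP 1 gives precedence to the SAP.

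Both documents plan for the dates to coincide. Protocol 8 has the first dose taken on site at the Baseline Visit, where randomization also takes place, and the Protocol synopsis starts darbepoetin alfa at Baseline/Day 1. Protocol 4.1 adds, however, that "ESA dosing is independent of the visit schedule, and the dosing schedule may shift per local standard of care and investigator discretion".

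For subjects who were never dosed, SAP 9.1 states that "the analysis will include individuals who never received treatment". Footnote a of SAP Table 1 provides that "If patient has no first dose date, day 1 will be the randomization date". The general convention in SAP 5 reads "For subjects whose reference date is missing, the study day will also be categorized as missing". Neither SAP 5.2 nor 9.2.1 repeats the footnote.

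**The concern.** The primary estimand compares treatment assignment in the randomized population. Baseline Hb enters that comparison twice: it is subtracted to form the endpoint (SAP 9.2.3), and it is an ANCOVA covariate (SAP 9.2.4). A covariate in such an analysis should be fixed before assignment. Under the SAP's rule it is fixed only if nobody's first dose comes late.

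The trial is open-label, and the only written latitude on dose timing concerns the control drug. Vadadustat is first given at the site at the Baseline Visit. If some control subjects start late, their baseline could include an Hb measured after assignment while they are off ESA, and their Weeks 20 to 26 window would slide later by the same number of days. None of the sensitivity analyses in SAP 9.2.5 uses a randomization anchor, so none would show the effect. SAP 10.2 does start Hb safety data at randomization, so the SAP uses two clocks for the same measurement.

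**Working it through.** **The plan's own figure.** Inputs from SAP 2.6: SD 1.2 g/dL, margin 0.75 g/dL, true difference 0, about 100 per arm, 30% dropout, 2-sided 95% CI. With 70 evaluable per arm, SE = 1.2 × √(2/70) = 0.203. Then 0.75/0.203 − 1.96 = 1.74, which gives power of 95.9%. The stated figure of more than 90% is reproduced. With both dates equal, neither definition changes it.

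**When a late first dose matters.** Let the first dose come k days after randomization, with visits kept on the schedule counted from randomization. Target days come from SAP Table 1 and visit tolerances from the Protocol schedule (±3 days at Weeks 2 and 4, ±5 days at Weeks 20 and 30). The study day counted from first dose is the target day minus k. Baseline takes values up to Day 1, and the primary window is Days 127 to 196.

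| Scheduled Hb | On target | Earliest allowed visit |
|---|---|---|
| Week 2 enters baseline | 14 − k ≤ 1, so k ≥ 13 | 11 − k ≤ 1, so k ≥ 10 |
| Week 4 also enters baseline | 28 − k ≤ 1, so k ≥ 27 | 25 − k ≤ 1, so k ≥ 24 |
| Week 20 leaves the primary window | 140 − k ≤ 126, so k ≥ 14 | 135 − k ≤ 126, so k ≥ 9 |
| Week 30 enters the primary window | 210 − k ≤ 196, so k ≥ 14 | 205 − k ≤ 196, so k ≥ 9 |

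At k = 14 the on-target Week 20 value falls on Study Day 126 and the Week 30 value on Day 196. An unscheduled central Hb in the gap could enter baseline after a shorter delay.

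**Size of the baseline effect.** Let f be the share of controls with one of their two baseline values taken after randomization, d the Hb drift in that value, and b the slope of primary-period Hb on baseline Hb. The control baseline mean moves by f × d/2. ANCOVA passes on b times that shift, so the bias in vadadustat minus darbepoetin is b × f × d/2. The documents give none of f, d and b. The ranges here are assumptions: f 5–30%, d −0.3 to −1.0 g/dL, b 0.3–1.0. Power is (0.75 + bias)/0.203 − 1.96 on the normal scale, with 70 evaluable per arm.

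- Smallest: 0.3 × 0.05 × (−0.3)/2 = −0.002 g/dL; power 95.8%.
- Middle: 0.5 × 0.20 × (−0.5)/2 = −0.025 g/dL; power 94.7%.
- Largest: 1.0 × 0.30 × (−1.0)/2 = −0.15 g/dL; power 84.1%.

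If Hb rises in the gap, d is positive and the bias favours vadadustat. The effect of the shifted primary window is not included in these figures.

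**Never-dosed subjects.** Footnote a gives them a Day 1. Eligibility (Protocol 5.2.1) requires two central Hb values in screening, so measured values exist, and SAP 9.2.1 accepts a single value. The gap is one of wording. SAP 5.2 and 9.2.1 name only the first dose date, and SAP 5 sets study day to missing when the reference date is missing.

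**The case against.** The strongest reply is that the problem needs conduct the protocol does not plan. Every arm is to start at the Baseline/Day 1 visit, and when that happens the two definitions pick the same values. The latitude in Protocol 4.1 directly follows the text on dose adjustment and can be read as covering ongoing dosing only, since it does not mention the first dose. The SAP's wording is the same for all arms. If Hb falls while a control subject waits, the baseline effect works against vadadustat, which is conservative for noninferiority.

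Much of this stands. It sets the expected effect at zero under planned conduct and makes the exposure of the control arm a possibility only. It does not remove the conflict: the SAP overrides the protocol's rule, and nothing in the SAP protects the covariate if a first dose does slip. Nor is the direction guaranteed.

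Three stronger readings are tempting and are not supported:

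- A reader might infer that never-dosed subjects have no baseline and that their measured Hb must be imputed. Footnote a, the existing screening values and the one-value rule say otherwise.
- A reader might infer that the intention-to-treat comparison is broken. Allocation and the analysis population are unchanged; the exposure is limited to late starters.
- A reader might take the shift in the control baseline mean as the bias, or assume that both baseline values are affected. In the middle case the mean shifts by 0.20 × 0.5/2 = 0.05 g/dL, but the treatment difference moves by half of that. Two affected scheduled values would need a delay of about 24 to 27 days.

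**Conclusion.** The conflict is real and should be corrected, but it is not a threat to the trial as planned. The SAP replaces a baseline fixed at randomization with one that can absorb a post-assignment Hb, and its windows move with the first dose. The effect is zero if dosing starts on the day of randomization, and a scheduled Hb reaches baseline only after a delay of about 10 to 13 days. Under the assumed ranges the baseline route moves the treatment difference by about 0.002 to 0.15 g/dL. The middle case of 0.025 is about 3% of the 0.75 g/dL margin. The sign depends on whether Hb falls or rises before the first dose. The result rests on assumed late-start rates, drift and slope, and on visits staying on the randomization schedule. For never-dosed subjects only a drafting gap remains.

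**What to change.** In SAP 5.2 and 9.2.1, restore the protocol's baseline for all randomized subjects: the average of the last two central Hb values on or before the randomization date, and not after the first dose. In SAP 5.1, count the Hb efficacy windows (the primary and secondary efficacy periods) from the randomization date. Keep the first-dose study day for exposure, adverse events and other safety summaries. Never-dosed subjects then need no special rule for Hb efficacy.

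The cost is SAP wording and a second study-day variable for Hb efficacy, with a statement of which outputs use which clock. No new data are needed, and the planned sample size and power do not change. If the first-dose anchor is kept, the least that should be done is to repeat footnote a in 5.2 and 9.2.1 and to add a randomization-anchored sensitivity analysis to 9.2.5.
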